COVID-IVIG Protocol Cover Page

Study Title: Randomized Open Label Study of Standard of Care Plus Intravenous Immunoglobulin(IVIG) Compared to Standard of Care Alone in the Treatment of COVID-19 Infection

NCT Number: NCT04411667

Document Date: 19May2020

Protocol name: COVID-IVIG

Principal Investigator: [name]; [contact]; [contact]
IRB # 2004902

Title: Randomized Open Label Study of Standard of Care Plus Intravenous Immunoglobulin (IVIG) Compared to Standard of Care Alone in the Treatment of COVID-19 Infection

Primary Objective:

1. To identify whether or not IVIG can halt the progression to respiratory failure requiring mechanical ventilation in subjects admitted to the hospital with confirmed COVID-19.

Secondary Objectives:

1. To identify whether adding IVIG to the standard of care will reduce days requiring oxygen therapy.
2. To identify whether adding IVIG to the standard of care will reduce total hospital days.

Hypothesis: We hypothesize that the addition of IVIG will be beneficial in abating acute lung injury in subjects with SARSCoV-2 induced hypoxia that results in organ injury in such patients.

Background: Coronaviruses has been known zoonotic pathogens since the early 1970's. Bats have been identified as the main natural reservoir and domesticated animal intermediary species (e.g., camels, cats) have facilitated transmission to humans. In late 2019, a novel coronavirus (SARS-CoV-2) emerged in humans, originating in Wuhan, China and spreading across the globe as a pandemic, causing coronavirus disease of 2019 (COVID-19).

The current mortality rate (17MAR2020) is not well described because of the shortage of laboratory testing assays worldwide. Using WHO data on the cumulative number of deaths to March 1, 2020, mortality rates would be 5.6% (95% CI 5.4–5.8) for China and 15.2% (12.5–17.9) outside of China⁸.

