Grave concerns are raised about the ability of the US healthcare system to handle the demand of subjects affected by the COVID-19 pandemic. While 80-85% of identified COVID-19 patients are asymptomatic or have mild disease, the 15-20% of patients requiring medical support (of which 1/3-1/2 are estimated to require ICU care) would pose dire consequences of healthcare access with current resources. Therefore, while the spread of virus continues to escalate, the ability to abort subjects away from the path of acute lung injury requiring mechanical ventilation would render an extreme advantage to healthcare systems. The average time from hypoxia to mechanical ventilation is nine days, and once patients become ventilated, they frequently require support for 2 weeks.

[figure not shown]
[figure not shown]
It is of interest that the natural history of COVID-19 frequently exhibits a biphasic illness seen with other acute viral and atypical infection. The first part of the illness is driven by direct viral

[figure not shown]
replication in permissive host tissues, which for COVID-19 is largely the respiratory tract. The host immune response to the primary infection results in a second phase, more catastrophic than the first, driven by immune system hyperactivity, often referred to as a ‘cytokine storm.’ Therefore, the successful treatment of more severe infection will likely rely more on immunomodulation rather than on antiviral therapy.¹ IVIG is an immunomodulatory agent used to treat the immunological complications of many infections, including immune-mediated encephalitis and Guillan-Barre.²

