1. Confirmed COVID-19 positive test result (including presumptive positive).
2. Hospitalization
3. Requiring ≥ 4 liters/min O_2 nasal cannula to maintain oxygen saturation $\geq 92\%$, but not mechanically ventilated
4. Age ≥ 18 years old.
5. Access to a phone in the hospital room or an electronic device that is capable of receiving phone calls and/or video calls and/or e-mail.
6. Able to read/write/speak English or Spanish fluently.
7. Subjects must have the capacity to provide consent or an appropriate Legally Authorized Representative (LAR) to provide informed consent.
8. Negative pregnancy test for women of childbearing potential.

Exclusion Criteria:

1. Severe allergy to any IVIG product formulation
2. History of DVT, PE, thromboembolic stroke or other thrombotic events

3. Hypersensitivity to corn. Octagam® contains maltose which is a sugar derived from corn.
4. Uncontrolled hypertension (SBP>180 mm Hg or DBP>120mmHg)
5. Active participant in another research treatment study
6. Mechanically ventilated patient
7. Code status is Do Not Resuscitate or Do Not Intubate

Age of Subjects: ≥18 years of age

Gender of Subjects: Either male or female

Racial and Ethnic Origin: Non-specific

Vulnerable Subjects: Hospitalized subjects

Study Design: Investigator initiated, open label, multicenter, two arm, randomized study to compare the impact of adding IVIG to the Standard of Care (SOC) to the SOC without IVIG. Randomization ratio will be 1:1.

Procedures and Study Visits:

1. The PI will be notified of a COVID-19 tested positive patient via hospital generated alert.
2. The PI or designee will prescreen the patient using the inclusion and exclusion criteria.
3. PI or Sub-I will contact the study team, if the patient passes prescreening.
4. The CRC will obtain an informed consent from the subject or LAR either electronically utilizing DocuSign® or with a paper copy utilizing an impartial witness:
 - a. The research team will utilize DocuSign® for the signing of the consents in order to be compliant with the infection control measures taken place for Highly Infectious Diseases. Below are the steps of the DocuSign® procedure:

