Study Timeframe: The study time frame would be from IRB approval date to the end of the pandemic or until our sites reach 40 subjects, whatever comes first. We anticipate that at the current COVID-19 rate, it should take about 6 weeks to enroll all patients from the time of study initiation.

The end of study for each individual subject will be the date of discharge from the Sharp HealthCare hospital. The subject will not be followed if there is a transfer to a non-Sharp hospital or any sub-acute care setting (i.e., SNF, LTAC, rehabilitation center). A subject's participation will also end if the subject's goals of care have transitioned to palliation, including changing the code status to Do Not Resuscitate or Do Not Intubate of which would render the patient no longer a candidate for intubation.

Method of Subject Identification and Recruitment: The PI or Sub-I will be notified of a COVID-19 confirmed positive patient via hospital generated alert as part of the Infectious Disease Team at each hospital.

Subject Capacity: Subjects who are cognitively impaired or lack the capacity to provide informed consent (as described in HRP-013 section 5.2) may be enrolled in the study if they have an appropriate LAR to provide written informed consent on their behalf. The researchers will follow the guidance outlined in HRP-013 "Legally Authorized Representatives (Surrogate Consent)" when obtaining surrogate consent.

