Data Collection/ Assessment Instruments: The Case Report Form will include the following data elements: Demographics (age, gender, race/ethnicity, insurance), medical status (pre-existing comorbid conditions (based on the Charlson Comorbidity Index), ferritin level (results will only be collected if lab is ordered as part of the subject's standard of care), CRP level. The tool used to calculate the Charlson Comorbidity Index can be found here <https://www.mdcalc.com/charlson-comorbidity-index-cci#next-steps>). Other data to be collected from standard of care procedures includes vital signs, result of blood or urine pregnancy test, serum creatinine, calculated creatinine clearance (Cockcroft and Gault equation), white blood cell count, platelet count, maximum body temperature in the past 24 hours and oxygen demand rate, whether or not there is an admission to the ICU, any concomitant antimicrobials including azithromycin, doxycycline, hydroxychloroquine, chloroquine, and remdesivir. Receipt of interventions will include standard of care in those who have tested positive for COVID-19. Measures of healthcare service utilization will include length of stay, number of days in ICU, number of days requiring oxygenation, discharge disposition and mortality.

Data Collection Resources: The Study Coordinator will complete the Case Report Forms, with assistance from Sharp's Clinical Analytics team to extract information from the EMR.

Data Analysis: Descriptive statistics will be conducted to describe frequencies of demographics and clinical characteristics including the following: age at discharge, gender, race/ethnicity, payer, comorbid conditions based on the Charlson Comorbidity Index, receipt of medical interventions (mechanical ventilation, medications) and healthcare service utilization (ICU admission and Length of Stay in the hospital). Frequencies and descriptive statistics will be conducted using chi-square or 2-tailed Fisher exact statistics depending on the final sample size for categorical data and t-tests for continuous data. Kaplan-Meier analysis will be performed with assistance from a biostatistician regarding the endpoints of mechanical ventilation and discharge to home endpoints. We do not anticipate number of patient deaths for be sufficient for a meaningful analysis.

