Privacy of Subjects: There will be limited access to the subject due to standard of care isolation protocols. The Informed Consent process will emphasize the personal nature and privacy

concerns related to communications regarding the subject's condition and infectious disease test results.

Confidentiality of Data and Storage: Subjects information will be recorded on a master list accessible to the investigator and research staff. It will be stored electronically on a secure server. Information included on master list: subject ID, hospital, date screened, patient name/room#, FIN, group, age, gender, enrollment status, telephone number, email address, and address. All binders will be stored and secured at Sharp's Center for Research office in accordance with all regulatory and organizational requirements, and will be accessed only by authorized personnel. No subject-specific data will be reported. Sharp FIN will be used to link subject records across data systems and hospital visits. Protected Health Information (PHI) will be safeguarded as specified by Sharp HealthCare policy. There is a risk of disclosure of PHI from inappropriate access to the study database. All efforts will be made to protect PHI, including password protecting the database with access only allowed to study members who are Sharp HealthCare employees. All datasets will be de-identified prior to any statistical analyses conducted by the Statistician. Identifiers will be destroyed two years after study end date, once data has been aggregated for reporting.

Data Monitoring: A designated person (or group of designees) who is not part of the Research Team will review and will report the outcomes to the SHC IRB after a total of 10, 20, and 40 patients (5, 10, and 20 in each arm, respectively) have completed/met the endpoint of the study. Additionally, if unexpected adverse outcomes are identified at any point in the enrollment the designated person will review the case on an individual basis.

Benefits to Individual Subjects: Potential reduction in ICU hospitalization, potential avoidance of mechanical ventilation and potential decrease in length of stay in the hospital.

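### Deaths should be reported by arm beside the ventilation result: the plan sets them aside on an expectation it never quantifies and its Background does not settle

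*Combined protocol and SAP*

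**What the plan says.** Procedures and Study Visits (item 8) makes death one of three endpoints, with discharge home and mechanical ventilation, and ends participation at whichever comes first. Data Collection/ Assessment Instruments lists "discharge disposition and mortality" among the items to be collected, and the data source is the hospital record (EMR).

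Data Analysis plans Kaplan-Meier analysis for ventilation and discharge home only. Of the third endpoint it says "We do not anticipate number of patient deaths for be sufficient for a meaningful analysis". No count, rate or threshold supports this. The outcomes it lists for descriptive summary are ventilation, medications, ICU admission and length of stay. Death is not among them.

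Two Background statements bear on the likely number: "mortality rates would be 5.6% (95% CI 5.4–5.8) for China and 15.2% (12.5–17.9) outside of China", and "the 15-20% of patients requiring medical support (of which 1/3-1/2 are estimated to require ICU care". The Background also warns that mortality was poorly characterised because tests were scarce.

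On size, recruitment runs to the end of the pandemic or "until our sites reach 40 subjects, whatever comes first". Study Design says "Randomization ratio will be 1:1", and Data Monitoring schedules reviews after "10, 20, and 40 patients (5, 10, and 20 in each arm, respectively".

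**The concern.** The primary objective is progression to mechanical ventilation. Intubation is a clinician's decision, and here the clinician knows the arm. A patient who dies without being intubated never becomes a ventilation event. With 20 per arm, each such patient is worth 1/20 = 5 percentage points of that arm's ventilation proportion. A lower ventilation count on IVIG could mean that fewer patients deteriorated, or that more of them died first. Without deaths by arm a reader cannot tell which.

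The other side of the event is also hidden. If observation stops at ventilation, nothing is learned about whether ventilated patients survived. The protocol rates the trial as greater than minimal risk and names venous thrombosis among the adverse reactions, so deaths by arm are a safety result as well.

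Finally, the only reason given for setting death aside is an expectation of small numbers, and nothing in the plan shows where it comes from.

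**Working it through.** **No stated figure.** The plan gives no expected number of deaths, no death rate for the enrolled population, no power and no alpha, so there is nothing to reproduce. What can be checked is the range its Background allows.

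**Inputs.** N = 40, 20 per arm (Study Timeframe, Study Design, Data Monitoring). Mortality 5.6% for China and 15.2% outside China, and 15-20% of identified patients needing medical support (Background). Enrolled patients are hospitalised on at least 4 L/min oxygen and not ventilated (inclusion criteria).

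**Expected deaths in 40**

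| Basis | 5.6% rate | 15.2% rate |
|---|---|---|
| Applied directly, 40 × rate | 40 × 0.056 = 2.2 | 40 × 0.152 = 6.1 |
| Scaled, share 20% | 5.6/20 = 28.0%; 11.2 deaths | 15.2/20 = 76%; 30.4 deaths |
| Scaled, share 15% | 5.6/15 = 37.3%; 14.9 deaths | 15.2/15 = 101%; 40.5 deaths |

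The scaled rows assume that all deaths occur among those needing support, that the mortality rates and the 15-20% share one denominator (the Background states none for the mortality rates), and that enrolled patients are typical of the supported group. The direct row probably errs low for the 5.6% rate, since it applies a general rate to patients selected for hypoxia. The last cell exceeds the number enrolled, so the scaling cannot be trusted as a forecast.

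**Sensitivity.** At 28%, the binomial probability of 5 or fewer deaths in 40 is 0.017. If the scaled rates are halved (an assumption) to 14.0% and 18.7%, the expected deaths are 5.6 and 7.5, and at 14% the probability of 5 or fewer is 0.50.

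**What the trial would observe.** All these figures are deaths over the whole illness. Under item 8 of Procedures and Study Visits, only deaths before ventilation or discharge home fall within participation. Study Timeframe removes patients further at transfer out or at a change to palliation or DNR/DNI. The in-study number will be lower and cannot be computed from the documents.

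**Precision** (two-sided alpha 0.05 and a halving of mortality are assumptions):

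- Control rate 28% to 37.3%, halved on IVIG, 20 per arm: power 11% to 17% by Fisher's exact test, 19% to 25% by normal approximation.
- By events at hazard ratio 0.5 (Schoenfeld): 21% with 11 deaths, 27% with 15. About 66 deaths are needed for 80%.
- If 28% to 37.3% is instead the rate over both arms combined: 17% to 27% by Fisher, 25% to 36% by normal approximation.
- Illustration: 9/20 v 3/20 is 45% − 15% = 30 points, Newcombe 95% interval 2 to 53, Fisher p = 0.08. That is suggestive at most, but a reader would need to see it.

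**Follow-up rules side by side**

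- Procedures and Study Visits, item 8: participation ends at the first of discharge home, ventilation or death.
- Study Timeframe: each subject's end of study is discharge from the Sharp hospital, but there is no follow-up after transfer to a non-Sharp hospital or sub-acute care, and participation ends at palliation or DNR/DNI.
- Termination of the Study: item 1 continues data collection to discharge when study treatment stops early; item 6 lists palliation or DNR/DNI.
- Secondary objective 2 (total hospital days) and the case report form items length of stay and discharge disposition need data to discharge, including for ventilated patients.

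These do not agree on whether a death after ventilation is recorded.

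**The case against.** The strongest reply is that the sentence is right in its own terms. It follows directly on the Kaplan-Meier plan for the other two endpoints, so it most naturally refers to death as a first event. Such deaths may well be few, because patients with DNR/DNI status are excluded at entry and participation ends at ventilation, palliation or a code-status change. Even 11 to 15 deaths would give low power. Fisher's test would need a split as extreme as 2 v 9 with 11 deaths (p = 0.031), or 4 v 11 with 15 (p = 0.048). Deaths are not ignored either: mortality is collected, and someone outside the research team reports outcomes to the IRB after 10, 20 and 40 patients.

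Most of this stands. A reader might infer that the Background implies 11 to 15 deaths and so contradicts the sentence. The documents do not support that: the figure comes from one of two quoted rates, under a method that fails on the other. Nor do they show that deaths would be about as common as ventilations, since the 1/3 to 1/2 figure is for ICU care. It also goes too far to call death immune to knowledge of the arm, because palliation, code status and transfer are bedside decisions that affect whether an in-hospital death is counted.

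What does not stand is the step from low power to no presentation. Low power argues against a confirmatory test, not against showing the counts. If few deaths are seen because observation stops at ventilation, that reflects the follow-up rule and gives no reason to leave mortality out. A report to the IRB does not put deaths beside the ventilation result.

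**Conclusion.** The point holds as an interpretive and reporting gap, not as a contradiction between Data Analysis and the Background. A named endpoint with a collected data field has no planned presentation by arm, and the reason given is unquantified. For 40 patients the Background is compatible with about 2 to 6 deaths, or about 11 to 15 under the scaling assumption for the 5.6% rate. It does not choose between them.

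The conclusion rests on design features rather than on the count: open-label treatment, a discretionary primary event, death before intubation leaving a patient out of the ventilation count, and participation ending at ventilation. Followed as written, the plan could report a ventilation benefit with no deaths by arm beside it. The size and direction of any resulting distortion cannot be computed from the documents.

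**What to change.** Replace the sentence on deaths in Data Analysis with:

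> All-cause in-hospital death, counted from the EMR to discharge from the Sharp hospital in every randomised patient, including after ventilation or a change in code status, will be reported by arm as counts and a risk difference with a 95% confidence interval next to the ventilation result. Deaths before ventilation will be shown separately and transfers out reported by arm. No power is claimed.

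Then reconcile the end-of-participation wording in Procedures and Study Visits (item 8), Study Timeframe and Termination of the Study, so that collecting outcome data to discharge is allowed after participation ends. This concerns outcome recording only, not treatment.

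**Cost.** A short passage in Data Analysis plus aligned wording in three other sections. Mortality, length of stay and discharge disposition are already on the case report form and come from the EMR, so no new procedure is needed. The price is a wide and probably inconclusive interval that has to be shown. Deaths after transfer out will still be missed, which is why transfers need reporting by arm. Item 8 also lets a patient join another protocol once an endpoint is reached, so deaths after ventilation may reflect other study treatments.

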Potential Benefits (Value) to Society: Any data collected will be a benefit to society whether we prove or disprove the hypothesis. However, if it is determined that the studied intervention indeed does reduce demand for mechanical ventilation and ICU care, it may provide significant relief to a medical care system that is anticipated to be overwhelmed at pandemic peak. The benefits will most likely be realized in the next SARS-CoV-2 epidemic. There are potential benefits to each institution that participates in this study to reduce the demand of mechanical ventilation and reduce the demand for isolated negative pressure ICU rooms.

Risk Category: Greater than minimal risk

Potential Risks: All of the adverse reaction and hypersensitivities are detailed in the package insert. These risks are also explained in layman's terms in the Informed Consent Form. The most common adverse reactions include the following: Headaches, allergic reaction and anaphylaxis, aseptic meningitis, venous thrombosis.

Protection Against Risks:

1. Pre-medicate with methylprednisolone IV to reduce/avoid infusion related reactions, including headache, aseptic meningitis.
2. The subject will be in the in-patient acute care setting with the Standard of Care monitoring as would be done if the drug were to be administered outside of the study setting.
3. If the subject experiences side effects that are suspected to be due to the IVIG for subjects in the study group, it will be up to the discretion of the treating clinician/PI whether to continue the IVIG or not.
4. There are no adequate and well-controlled studies of methylprednisolone in pregnant women, and it is not known whether Octagam 10% can cause fetal harm when administered to a pregnant woman or can affect reproduction capacity. Therefore, pregnant women are excluded from participation, and women of childbearing potential will undergo a blood or urine pregnancy test prior to randomization.

Termination of the Study:

1. If the subject prematurely stops study treatment, the study team will continue to collect data until discharge.
2. If the subject progresses into mechanical ventilation, those who are actively receiving IVIG will be stopped.
3. If there are additional doses schedule per protocol and the subject has progressed into the intensive care unit, the additional doses will not be administered.
4. The patient retain the right to terminate the study drug for any reason.
5. Discharge to home

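### The plan does not provide for collecting the IVIG reactions it names, thrombosis above all, or for reporting them by arm, and its review rules do not clearly cover them.

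*Combined protocol and SAP*

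**What the plan says.** **Named risks.** Potential Risks lists the most common reactions: "Headaches, allergic reaction and anaphylaxis, aseptic meningitis, venous thrombosis". Exclusion criterion 2 removes patients with "History of DVT, PE, thromboembolic stroke or other thrombotic events". Risk Category puts the trial above minimal risk, and Study Design makes it open label with 1:1 allocation.

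**Data collected.** Data Collection/Assessment Instruments opens with "The Case Report Form will include the following data elements" and then itemises them. The items nearest to safety are vital signs, serum creatinine, "white blood cell count, platelet count, maximum body temperature in the past 24 hours and oxygen demand rate", and ICU admission. The utilisation measures are "length of stay, number of days in ICU, number of days requiring oxygenation, discharge disposition and mortality". Data Sources gives the hospital electronic medical record (EMR) as the origin of the data.

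**Analysis.** Data Analysis covers demographics, comorbidity, interventions received, ICU admission and length of stay, with Kaplan-Meier analysis of ventilation and discharge home. It mentions no adverse event.

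**Monitoring.** Under Data Monitoring, someone independent of the study staff "will review and will report the outcomes to the SHC IRB after a total of 10, 20, and 40 patients"; the numbers per arm at those reviews are half of these totals. The next sentence adds the ad hoc rule: "if unexpected adverse outcomes are identified at any point in the enrollment the designated person will review the case on an individual basis".

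**Suspected side effects.** Protection Against Risks, item 3, covers the IVIG arm only. It leaves continuation of IVIG to the clinician and sets no recording rule.

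**The concern.** The protocol treats thrombosis as a real hazard: it lists it as a risk and excludes patients with a thrombotic history. Yet the sections that decide what is recorded, analysed and reviewed do not pick it up. The trial could report fewer ventilations with no planned count of thromboses in either arm. The designated person would reach the reviews at 10 and 20 patients without tabulated harm data. Thrombosis is also the named event for which a control rate matters most, because a thrombosis in one IVIG patient cannot be interpreted without knowing how often it occurs under standard of care. Case-by-case reports do not supply that rate.

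**Working it through.** The plan gives no figure on this point, so there is none to reproduce. Steps 1 to 3 compare the text; step 4 is arithmetic under assumed rates.

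**Step 1. Named reactions against the form and the analysis.**

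| Reaction (Potential Risks) | Form field | In Data Analysis | Nearest collected item |
|---|---|---|---|
| Headache | none | no | none |
| Allergic reaction, anaphylaxis | none | no | vital signs |
| Aseptic meningitis | none | no | maximum temperature, white cell count |
| Venous thrombosis | none | no | platelets, ICU admission, mortality |

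That is 0 of 4 on the form and 0 of 4 in the analysis. The nearest items are non-specific and would not identify any of these events.

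**Step 2. Review rules.** The ad hoc trigger is worded for unexpected outcomes. The term is not defined, but a reaction printed in the protocol's own risk list is, in ordinary use, expected. The 10/20/40 reviews report outcomes, also undefined. Procedures and Study Visits, item 8, sets three endpoints (discharge home, ventilation, death), and the reviews are timed to patients who have completed or met the endpoint, so the endpoints are the likelier meaning. On the broader meaning, the itemised form still gives the designated person no adverse-event data.

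**Step 3. Observation window.** Three places bear on how long harms could be recorded:
- Procedures and Study Visits, item 8: participation ends at discharge home, ventilation or death.
- Study Timeframe: each subject's end of study is hospital discharge. There is no follow-up after transfer, and participation also ends on a move to palliation.
- Termination of the Study, item 1: after early stopping of treatment, data continue to be collected until discharge.

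If recording stops at ventilation in some patients and runs to discharge in others, event counts depend on time observed as well as on treatment.

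**Step 4. What a by-arm table could deliver.** Inputs: 40 subjects (Study Timeframe) at 1:1 (Study Design), so 20 per arm. Assumptions: two-sided alpha of 0.05 (the plan states none) and the illustrative event rates below.

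- Chance of at least one event among n patients in one arm, 1 − (1 − p)^n:

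| True rate p | n = 5 | n = 10 | n = 20 |
|---|---|---|---|
| 2% | 9.6% | 18.3% | 33.2% |
| 5% | 22.6% | 40.1% | 64.2% |
| 10% | 41.0% | 65.1% | 87.8% |

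- Upper 95% limit when 0/20 is observed: two-sided 1 − 0.025^(1/20) = 16.8%; one-sided 1 − 0.05^(1/20) = 13.9%.
- Smallest IVIG count reaching p < 0.05 by two-tailed Fisher when standard of care has 0/20: 4/20 gives p = 0.106 and 5/20 gives p = 0.047, so five events are needed.
- Fisher power at 20 per arm, by exact binomial enumeration: 5% vs 10%, 1.7%; 5% vs 20%, 16.8%; 10% vs 30%, 24.2%; 5% vs 30%, 44.6%. (The power of 16.8% matches the upper limit above by coincidence.)
- Sample size for 80% power at 5% vs 20%, by the usual two-proportion approximation: 76 per arm.

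The first two results describe a single arm. The last three concern the comparison, and they show that it would be weak.

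**The case against.** A reader might infer that monitoring looks at nothing but unexpected events. The text does not support that. The ad hoc rule is an addition to the scheduled reviews by someone outside the research team, and because their outcomes are undefined, coverage of harms is unclear rather than excluded. Mortality and ICU admission are collected in any case.

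A reader might also infer that the named harms can never be compared between arms. That too goes beyond the documents. Data come from the EMR for both arms, records are linked across hospital visits, and identifiers are kept until two years after study end. Charted thromboses could be retrieved retrospectively. What remains is that nothing prespecifies definitions, dates or a window. Retrieval in an open-label trial, where side effects are mentioned only for the IVIG arm, is open to unequal ascertainment and would come after the reviews at 10 and 20 patients.

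Reading *unexpected* as leaving out the listed risks is an inference, since the term is undefined. It is the plain reading, and the remedy for an unclear trigger is the same.

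The objection on power stands in full: with 20 per arm the table cannot establish whether IVIG raises thrombosis. It also stands that infusion reactions are informative mainly in the IVIG arm, because standard-of-care patients receive no study infusion.

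**Conclusion.** The point holds as a gap in planned collection and reporting. None of the four named reactions has a form field or a planned summary, the ad hoc trigger on a plain reading leaves them out, and the scheduled reviews do not say whether they include them. In an open-label trial above minimal risk this should be corrected.

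The gain is modest: a descriptive count in each arm. Observing 0/20 would still be compatible with rates up to 16.8% (two-sided 95%), and power is about 17% at an assumed 5% vs 20%. The event rates and the alpha are assumptions, not figures from the plan. The consent form and one part of the protocol before the eligibility criteria were not available for this check; the data collection, analysis and monitoring sections were.

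**What to change.** 1. **Trigger.** Extend the ad hoc review rule in Data Monitoring to any risk listed under Potential Risks, in addition to unexpected adverse outcomes.
2. **Form.** Add dated, EMR-extracted fields with short definitions for the named reactions, above all thrombotic events, in both arms from randomisation.
3. **Window.** Use one common observation window in both arms. To set it, reconcile Procedures and Study Visits item 8, Study Timeframe, and Termination of the Study, which differ on whether data stop at ventilation or run to discharge.
4. **Reporting.** Define the outcomes reported at the 10, 20 and 40 reviews so that they include these counts by arm, and repeat the table in the final report. Label it descriptive, and note that infusion reactions are informative mainly in the IVIG arm.

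Cost: a few form fields, one table and slightly more coordinator time, with no added tests or procedures. Reconciling the window also requires a small protocol clarification.
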